9.2. Compensation

² Philips Threshold PEP: https://www.usa.philips.com/healthcare/product/HCHS735010/treshold-positive-expiratory-pressure-device/overview

Document ID:	SRC_SLE_Sparkle EP 2_2021_11315	Document title:		Classification:	Confidential
Modified:	12 May 2021	Clinical Investigation Proto	Clinical Investigation Protocol ICH E6 Aligned		
Version:	1	User Tool ID:	16.2.6UserTool0004		
Status:	FINAL	User Tool Version Date	5June2019	Page:	22

¹ Philips Threshold IMT: https://www.usa.philips.com/healthcare/product/HCHS730010/treshold-inspiratory-muscle-trainer

Participants will be compensated \$50 for the office visit and \$225 for the data collection visit (\$275 in total). Participants who opt to discontinue from the study will be prorated at the time of withdrawal.

9.3. Safety Assessments

All study procedures will take place during study visits, under the supervision of the PI. The PI is a physician and all visits will take place at a clinical facility, allowing for clinical intervention if needed. The risks associated with the study are immediate; that is, it is considered highly unlikely that an AE will take place after the completion of a study visit.

If any participants discontinue or withdraw early, for any reason including AEs, the reason will be captured.

10. RISK/BENEFIT ASSESSMENT

10.1. Known potential risks

- There may be discomfort related to insertion and continued placement of the esophageal cannula.
 This could include a nose bleed, gagging, and/or vomiting.
- Dizziness, lightheadedness, a feeling of nausea, or fainting may occur during the fasting period.
- Dizziness/lightheadedness may occur during the data collection period, particularly during the different breathing conditions.
- The only anticipated AE related to the DreamKit device is skin irritation associated with the adhesive patch.
- There are no anticipated AEs related to the breathing devices (Philips IMT and Philips Threshold PEP), beyond the possible dizziness/lightheadedness described above.
- There are no anticipated AEs related to the Mexameter skin probe.

10.2. Known potential benefits

Participation in this trial will not result in direct benefit to the participant. The information collected from participants will be used to improve product design and function.

10.3. Assessment of Potential Risks and Benefits

- Participants reporting a sensitive gag reflex or dyspnea will not be recruited.
- If a participant experiences any adverse event related to fasting, they may discontinue the protocol and will be provided with food/juice.

Document ID:	SRC_SLE_Sparkle EP 2_2021_11315	Document title:		Classification:	Confidential
Modified:	12 May 2021	Clinical Investigation Protocol ICH E6 Aligned			
Version:	1	User Tool ID:	16.2.6UserTool0004		
Status:	FINAL	User Tool Version Date	5June2019	Page:	23

- If a participant experiences any discomfort related to dizziness or lightheadedness, they may return to relaxed breathing or discontinue the protocol at any time.
- Participants reporting a history of allergic reactions to medical adhesives will not be recruited.

It is the opinion of the Sponsor and the Principal Investigator (PI) that the benefits of this protocol outweigh the risks.

11. SAFETY MONITORING

11.1. Adverse Events and Serious Adverse Events

11.1.1. Definition of Adverse Events

An adverse event (AE) is any untoward medical occurrence associated with the use of an intervention in humans, whether or not considered intervention-related (21 CFR 312.32 (a)). When an AE is deemed to be related to the study device, it is termed an adverse device event.

11.1.2. Definition of Serious Adverse Events

An AE or suspected adverse reaction is considered serious if, in the view of either the investigator or Sponsor, it results in any of the following outcomes: death, a life-threatening AE, inpatient hospitalization or prolongation of existing hospitalization, a persistent or significant incapacity or substantial disruption of the ability to conduct normal life functions, or a congenital anomaly/birth defect. Important medical events that may not result in death, be life-threatening, or require hospitalization may be considered serious when, based upon appropriate medical judgment, they may jeopardize the participant and may require medical or surgical intervention to prevent one of the outcomes listed in this definition. When a serious AE is deemed to be related to the study device, it is termed a serious adverse device event (SADE).

11.2. Unanticipated Adverse Device Event

An unanticipated adverse device event (UADE) is defined in 21 CFR Part 812.3(s) as "any serious adverse effect on health or safety or any life-threatening problem or death caused by, or associated with, a device, if that effect, problem, or death was not previously identified in nature, severity, or degree of incidence in the investigational plan or application (including a supplementary plan or application), or any other unanticipated serious problem associated with a device that relates to the rights, safety, or welfare of subjects".

Other important medical events which may not result in any of the outcomes above, but which may require intervention to prevent one of the outcomes above, may in the opinion of the investigator, be considered a UADE.

11.3. Classification of an Adverse Event or Adverse Device Event

Document ID:	SRC_SLE_Sparkle EP 2_2021_11315	Document title:		Classification:	Confidential
Modified:	12 May 2021	Clinical Investigation Proto	Clinical Investigation Protocol ICH E6 Aligned		
Version:	1	User Tool ID:	16.2.6UserTool0004		
Status:	FINAL	User Tool Version Date	5June2019	Page:	24

11.3.1. Severity of Event

All AEs will be assessed by the study clinician using a protocol defined grading system as follows:

- Mild Events require minimal or no treatment and do not interfere with the participant's daily activities.
- Moderate Events result in a low level of inconvenience or concern with the therapeutic measures.
 Moderate events may cause some interference with functioning.
- Severe Events interrupt a participant's usual daily activity and may require systemic drug therapy
 or other treatment. Severe events are usually potentially life-threatening or incapacitating. Of note,
 the term "severe" does not necessarily equate to "serious".

11.3.2. Relationship to the Study or Device

All AEs will have their relationship to study procedures and the study device assessed by the clinician who examines and evaluates the participant based on temporal relationship and his/her clinical judgment. The degree of certainty about causality will be graded using the categories below.

- Definitely Related An AE is definitely related to study participation if it is clear that the event was
 caused by study participation. A definitely related event has a strong temporal relationship and an
 alternative cause is unlikely.
- Probably Related An AE is probably related when there is a reasonable possibility that the event
 is likely to have been caused by study participation. The AE has a timely relationship to the study
 procedure(s) and follows a known pattern of response, but a potential alternative cause may be
 present.
- Possibly Related An AE is possibly related when there is a reasonable possibility that the event
 might have been caused by study participation. A possibly related event may follow no known
 pattern of response and an alternative cause seems more likely. In other circumstances there may
 be significant uncertainty about the cause of the event, or a possible relationship to study
 participation cannot reasonably be ruled out.
- Unrelated An AE is unrelated if the cause is known and the event is in no way related to any
 aspect of study participation. If there is any uncertainty regarding AE causality then the event must
 be assessed as possibly related to research participation and reported to the IRB as indicated.
 Often, the cause of an unrelated AE is disease progression.

11.3.3. Expectedness

The PI will be responsible for determining whether an AE is expected or unexpected. An AE will be considered unexpected if the nature, severity, or frequency of the event is not consistent with the risk information previously described for the study intervention.

Document ID:	SRC_SLE_Sparkle EP 2_2021_11315	Document title:		Classification:	Confidential
Modified:	12 May 2021	Clinical Investigation Protocol ICH E6 Aligned			
Version:	1	User Tool ID:	16.2.6UserTool0004		
Status:	FINAL	User Tool Version Date	5June2019	Page:	25

11.4. Adverse Event Assessment and Follow-Up

Within 1-2 days of completing Visit 2, a phone call will allow for the assessment of any possible AEs that may have become apparent in the intervening period. Events will be followed for outcome information until resolution or stabilization

All AEs including local and systemic reactions will be captured on the appropriate case report form (CRF). Information to be collected includes event description, time of onset, clinician's assessment of severity, relationship to study product (assessed only by those with the training and authority to make a diagnosis), and time of resolution/stabilization of the event. All AEs occurring while on study must be documented appropriately regardless of relationship. All AEs will be followed to adequate resolution.

Any medical condition that is present at the time that the participant is screened will be considered as baseline and not reported as an AE. However, if the study participant's condition deteriorates at any time during the study, it will be recorded as an AE.

Changes in the severity of an AE will be documented to allow an assessment of the duration of the event at each level of severity to be performed. AEs characterized as intermittent require documentation of onset and duration of each episode.

11.5. Serious Adverse Event or Serious Adverse Device Event Reporting

The study investigator shall complete a SAE or UADE Form and submit to the Sponsor and to the reviewing IRB as soon as possible, but in no event later than 24 hours (for a SAE) or 10 working days (for an UADE) after the investigator first learns of the effect. The Sponsor is responsible for conducting an evaluation of the SAE/UADE and shall report the results of such evaluation to the Food and Drug Administration (FDA) and to all reviewing IRBs and participating investigators within 24 hours (for a SAE) or 10 working days (for a UADE) after the Sponsor first receives notice of the effect. Thereafter, the Sponsor shall submit such additional reports concerning the effect as FDA requests.

11.6. Device Deficiency

All device deficiencies, use or user errors, and equipment failures will be documented. Use or user errors will be captured as part of the source documentation. Device deficiencies and equipment failures will be kept on a separate log. The serial numbers and type of deficiency/failure will be captured. Unanticipated device deficiencies that lead or may lead to an SAE will be reported to the Sponsor within 24 hours of learning of the event.

11.7. Unanticipated Problems

Document ID:	SRC_SLE_Sparkle EP 2_2021_11315	Document title:		Classification:	Confidential
Modified:	12 May 2021	Clinical Investigation Protocol ICH E6 Aligned			
Version:	1	User Tool ID:	16.2.6UserTool0004		
Status:	FINAL	User Tool Version Date	5June2019	Page:	26

11.7.1. Definition of Unanticipated Problems

An unanticipated problem (UP) is any incident, experience, or outcome that for which the nature, severity, or frequency is unexpected for the subject population or research activities as described in the current IRB approved protocol, supporting documents, and the ICF.

11.7.2. Unanticipated Problem Reporting

The PI will submit to the Sponsor and to the reviewing IRB a report of any UADE occurring during an investigation as soon as possible, but in no event later than 10 working days after the investigator first learns of the effect (21 CFR 812.150(a)(1)). Under 812.46(b), the Sponsor shall report the results of such evaluation to the FDA and to all reviewing IRB's and participating investigators within 10 working days after the Sponsor first receives notice of the effect. Thereafter the Sponsor shall submit such additional reports concerning the effect as FDA requests (21 CFR 812.150(b)(1)).

12. STATISTICAL CONSIDERATIONS

The statistical analysis plan has been incorporated into this protocol. It is not a stand-alone document.

12.1. Sample Size Determination

Up to 20 participants will be enrolled. The evaluable dataset will consist of data from ten participants.

12.2. Statistical Analyses

12.2.1. General Considerations

The primary and secondary analyses will be performed in the validation dataset only. Descriptive data tables will be provided for all variables of interest. Continuous data will be presented by mean, standard deviation, median, minimum, and maximum observation. Data will be presented in the untransformed and transformed format (if applicable) for each continuous variable. Categorical data will be presented as frequencies and percentages. If formal statistical analysis is required, it will be performed using either SAS® or SPSS® software. Significance tests will be conducted at a two-sided significance level of alpha=0.05.

There are no statistical criteria for terminating the study. No sensitivity analyses are planned, and any deviations from the original statistical plan will be noted in the analysis report.

12.2.2. Participant Disposition

Participant disposition, including the total number of participants enrolled, completed, early terminations and withdrawals, will be presented. A listing will be provided with the reasons for discontinuation.

Document ID:	SRC_SLE_Sparkle EP 2_2021_11315	Document title:	Document title:		Confidential
Modified:	12 May 2021	Clinical Investigation Proto	Clinical Investigation Protocol ICH E6 Aligned		
Version:	1	User Tool ID:	16.2.6UserTool0004		
Status:	FINAL	User Tool Version Date	5June2019	Page:	27

12.2.3. Demographics and Baseline Characteristics

Participant demographics and baseline characteristics will be summarized for all participants enrolled and for evaluable participants.

12.2.4. Analysis of the Primary Efficacy Endpoint

The primary endpoint is the ICC of the peak-to-peak breath amplitude sequences extracted from the DreamKit and esophageal manometry respiratory effort signals among periods of occluded inspiration, end-expiratory breath holds, increased inspiratory resistance, increased expiratory resistance, and unresisted shallow breathing. We hypothesize that the lower-bound of the 95% confidence interval for the correlation of breath amplitude sequences extracted from the DreamKit and esophageal manometry respiratory effort signals will be ≥0.5.

Among the periods of occluded inspiration, end-expiratory breath holds, increased inspiratory resistance, increased expiratory resistance breathing and unresisted shallow breathing conditions, the peak-to-peak amplitude in the respiratory excursions will be extracted from the esophageal pressure signal and the DreamKit device signal. A correlation coefficient will be generated in order to compare the breath amplitude sequences from the two signals among these data collection periods. First, amplitudes of the DreamKit device signal will be scaled to have the same variance as the amplitudes calculated from the esophageal pressure signal. After this normalization step, amplitudes will be aggregated among all participants, and ICC estimates and their 95% confidence intervals will be calculated based on single measurements, absolute agreement and a 2-way mixed-effects model.⁵

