4. OBJECTIVES

4.1. Primary Objective, Endpoint, and Hypothesis

The objective of this study is to validate the DreamKit plethysmography-derived respiratory effort signal against the gold standard, esophageal pressure, in ten healthy participants during a single in-laboratory daytime visit.

The primary endpoint is the intraclass correlation coefficient (ICC) of the peak-to-peak breath amplitude sequences extracted from the DreamKit and esophageal manometry respiratory effort signals during periods of occluded inspiration, end-expiratory breath holds, increased inspiratory resistance, increased expiratory resistance, and unresisted shallow breathing. We hypothesize that the lower-bound of the 95% confidence interval for the correlation of breath amplitude sequences extracted from the DreamKit and esophageal manometry respiratory effort signals will be ≥0.5, representing at least moderate agreement between the signals.⁵

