4.3. Claims and Intended Performance

The proposed intended use statement for DreamKit is as follows, with the parts relevant to this study bolded (wording may change before regulatory submission):

The DreamKit device is a physiologic data recorder intended to collect and record data for use by clinical software used in polysomnography and sleep disorder studies for the diagnosis of sleep related breathing disorders. The Plethysmography-Acquired Respiratory Effort (PARE) algorithm provides a respiratory effort signal acquired from the DreamKit photoplethysmography signal that correlates with traditional respiratory effort signals used in polysomnography. The DreamKit with PARE provides the information required to detect apneas and hypopneas and classify these respiratory events as central, mixed, or obstructive. It is intended for adult use and can be used in a hospital, clinic, or patient home.

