5.2.5. Identification of performance target

We adopted a performance target of 0.5 for the ICC of respiratory effort amplitude between the DreamKit and esophageal manometry signals in order to demonstrate 95% confidence of at least moderate agreement between signals.⁶

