6.5. Strategies for Recruitment and Retention

The participants will be of both sexes, with a wide body mass index (BMI) range, in order to support generalizability of results. Due to the small sample size, no firm parameters for these measures have been determined a priori.

It is anticipated that racial/ethnic minorities will represent at least 30% of the sample.

All participants will be enrolled within the US. Recruitment will be the responsibility of the site, and will take place through a local university newspaper and online advertisements. As this study involves only two visits, it is not likely that participants will drop-out or be lost to follow-up before study completion. No specific strategies for retention are required.

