Data from the DreamKit device will not be visible in real-time, and therefore it is important to ensure that the DreamKit signals can be synchronized to the esophageal pressure signals post-hoc. At the beginning and end of the data collection period, the participant will be asked to breathe out and hold their breath for approximately three seconds; then take a deep breath in and hold for approximately three seconds; and then finally, tap the DreamKit device to coincide with the peak of inhalation. This process will place a motion artefact on the accelerometry signal timed (approximately) to inhalation observed in the respiratory effort and esophageal pressure signals. The SpO₂ signals collected via the Alice 6 and the DreamKit device may also be used for time-alignment. During data processing, it may be necessary to make a small adjustment to the DreamKit time to match the Alice 6 time, ensuring synchronization of the signals.

Data Collection

Participants will be instructed to undertake the following breathing conditions (all in the supine position):

- End-expiratory breath holds to mimic central apneas: ten breath holds after exhalation, 10-20 seconds in duration.
- Occluded inspiration to mimic obstructive apneas: five periods of occluded inspiration paced at 15 attempted breaths/minute with blocked nose and mouth closed, 10-20 seconds in duration.
- Increased inspiratory resistance to mimic obstructive hypopneas and RERAs: paced at 15 breaths/minute against inspiratory resistance using the Philips IMT device (see details below), for 30 seconds at a time, five times.
- Increased expiratory resistance to mimic obstructive hypopneas and RERAs: paced at 15 breaths/minute against expiratory resistance using the Philips Threshold PEP device (see details below), for 30 seconds at a time, five times.
- Shallow breathing to mimic central hypopneas: partial breaths paced at 15 breaths/minute without resistance, for 30 seconds in duration, five times.
- Slow: paced at 12 breaths/minute; two minutes.
- Fast: paced at 20 breaths/minute; two minutes.
- Relaxed: paced at 15 breaths/minute; two minutes.

The coordinator will allow the participant time to become comfortable and still before beginning each condition, and will note the exact start/end time of each (MM:SS) from the computer used for data collection.

The participant may return to relaxed breathing at any time if they experience discomfort or dizziness.

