For the paced breathing conditions, the site coordinator will play a metronome (e.g. www.imusic-school.com/en/tools-online-metronome) set to 24 (slow), 30 (relaxed) and 40 tones per minute (fast), allowing the participant to time each inspiration and expiration to the tones for breathing rates of 12, 15, and 20 breaths per minute.

Document ID:	SRC_SLE_Sparkle EP 2_2021_11315	Document title:		Classification:	Confidential
Modified:	12 May 2021	Clinical Investigation Protocol ICH E6 Aligned			
Version:	1	User Tool ID:	16.2.6UserTool0004		
Status:	FINAL	User Tool Version Date	5June2019	Page:	21

Increased inspiratory resistance will be achieved with the Philips Threshold IMT breathing trainer, a small, hand-held mouthpiece containing a flow-independent one-way valve¹. Similarly, increased expiratory resistance will be achieved with the Philips Threshold PEP device, a device which creates positive pressure during exhalation². The pressure of each device can be adjusted in 2cmH₂O increments. During data collection, the coordinator should coach the participant and adjust the pressure of each device when necessary in order to achieve appropriate changes in pressure during increased inspiratory and expiratory resistance conditions. Participants should aim to achieve a change from normal breathing of at least -15mmHg, but ideally -20 to -30mmHg, during the increased inspiratory and expiratory resistance conditions, and ensure a minimal change in esophageal pressure during the end-expiratory breath holds compared to normal breathing. A previous study following similar methodology to simulate apneas found a median change in esophageal pressure compared to normal breathing of -20.1mmHg (quartiles -21.9 to -15.0) with increased inspiratory resistance, -29.1mmHg (quartiles -38.4 to -20.6) with increased expiratory resistance, and 0.1mmHg (quartiles -2.9 to 2.0) with end-expiratory central apnea.^{10,11}

The data collection period is likely to be approximately one hour per participant, and will not exceed 1.5 hours. At this time, all equipment will be removed and the participant will be free to leave the laboratory.

Data processing

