Using the timing information noted during data collection, an analyst blinded to the DreamKit data will score the esophageal pressure data files in order to identify the periods of occluded inspiration, end-expiratory breath-holds, increased inspiratory resistance, increased expiratory resistance, shallow breathing, slow respiration, fast respiration, and relaxed breathing. Periods of poor pressure signal quality will be excluded from analyses, such as artifact caused by movement, swallowing, or sensor displacement. An independent analyst will then import the DreamKit signal and ensure that the two data sources (Alice 6 and DreamKit) are synchronized following the procedures above. Periods where the DreamKit device indicates poor effort data quality by means of channel fail events will be excluded from analyses.

Follow-up phone call

A follow-up phone call will be placed 1-2 days after completion Visit 2, in order to assess any AEs that may have become apparent in the intervening period.

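### The deciding 95% interval takes pooled breaths, not the ten participants, as its sample size, so its lower bound may not carry the stated confidence

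*Combined protocol and SAP*

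**What the plan says.** Under section 12.2.4, DreamKit amplitudes are first rescaled to the variance of the esophageal amplitudes. Then "amplitudes will be aggregated among all participants, and ICC estimates and their 95% confidence intervals will be calculated based on single measurements", for absolute agreement under a two-way mixed-effects model. No participant effect and no cluster-robust, bootstrap or repeated-measures interval is named.

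Section 4.1 puts the hypothesis as "We hypothesize that the lower-bound of the 95% confidence interval for the correlation of breath amplitude sequences" and requires that bound to be at least 0.5. Section 5.2.5 explains that the target was chosen "in order to demonstrate 95% confidence of at least moderate agreement between signals".

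Section 12.1 fixes ten evaluable participants without a calculation. Section 12.2.1 sets a two-sided alpha of 0.05 and plans no sensitivity analyses. Section 12.2.5 repeats the ICC for each participant, as an exploratory analysis only.

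On the reach of the result, the draft intended-use statement in section 4.3 ends "It is intended for adult use and can be used in a hospital, clinic, or patient home", and section 6.5 recruits both sexes "with a wide body mass index (BMI) range, in order to support generalizability of results".

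**The concern.** With two signals, the two factors of the ICC are breath and signal. Participant is not in the model, so the interval's sample size is the number of breaths, while the units actually sampled are ten people.

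Two sources of error are left out: the device may track effort better in some people than in others, and successive breaths in one person may resemble each other. If either is present and the mean offset is small, the interval is too narrow and a borderline device passes too often.

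The plan matches variances but not means, so a mean offset between the signals can remain. The interval then becomes very wide, and a device with adequate agreement can fail. Nothing else in the plan protects the decision, because the per-participant ICCs do not enter the deciding bound.

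**Working it through.** **Sample size used by the interval.** Section 9.1.3 specifies "five periods of occluded inspiration paced at 15 attempted breaths/minute with blocked nose and mouth closed, 10-20 seconds in duration", which is 5 × (10 to 20 s) × 15/60 = 12.5 to 25 breaths. Inspiratory resistance, expiratory resistance and shallow breathing each give 5 × 30 s × 15/60 = 37.5, together 112.5. The total is 125 to 137.5 per participant, or 1,250 to 1,375 for ten. One amplitude per breath hold (an assumption; the plan does not define it) adds 100, giving 1,350 to 1,475. All counts are before exclusions.

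**What passes.** By Fisher z with N = 1,400, the smallest passing ICC is tanh(atanh 0.5 + 1.96/√1398.5) = 0.538. With an effective N of 100 or 50 it would be 0.633 or 0.681.

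**Hand check.** Take 10 × 130 = 1,300 breaths and a between-person Fisher-z SD of τ. The interval uses SE = 1/√1298.5 = 0.0278. The real SE is about √(0.0278² + τ²/10). At a true ICC of 0.50, false pass ≈ P(Z > 1.96 × 0.0278 / real SE). For τ = 0.2 the real SE is √(0.0278² + 0.0632²) = 0.0691, the ratio is 0.79, and false pass is about 22%.

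**Simulation, simple model.** X is standard normal and Y = ρᵢX + √(1−ρᵢ²)E, with ρᵢ = tanh(μ + τN(0,1)). Y is variance-matched within participant. The interval is the F-based one for the single-measurement, absolute-agreement ICC. There is no offset, the true ICC is 0.50, and 4,000 replicates were run. The nominal false-pass rate is 2.5%.

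| τ (assumed) | 95% of individual ICCs | Hand check | Simulated false pass | Coverage |
|---|---|---|---|---|
| 0 | all 0.50 | 2.5% | 3.0% | 95% |
| 0.05 | 0.42–0.57 | 4.4% | 4.9% | 91% |
| 0.1 | 0.34–0.64 | 9.8% | 11.5% | 79% |
| 0.2 | 0.17–0.74 | 22% | 22.3% | 57% |
| 0.3 | 0.00–0.83 | 29% | 30.0% | 43% |

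The plan's 95% is therefore recovered when breaths are independent (τ = 0). If section 5.2.5 is read as one-sided (5%), the excess starts at τ of about 0.05 to 0.06.

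**Below the boundary.** At true ICC 0.45 / 0.40 the planned interval passes 0.4 / 0.0% (τ = 0.1), 4.2 / 0.4% (τ = 0.2) and 12.2 / 3.0% (τ = 0.3).

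**Other forms of dependence.** First-order serial correlation of 0.3 / 0.5 / 0.7 alone gives 4.2 / 8.4 / 15.0% false pass. In a different model (10 × 140 breaths), where participants account for 5 / 10 / 20 / 30% of the variance in both amplitude and device error, coverage is 92 / about 83 / 60–64 / 48–51%. This holds whether scaling is pooled or per participant.

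**Mean offset.** With matched unit variances and an offset of d SD, ICC = ρ/(1 + d²/2). For d = 0.5 and ICC 0.65, ρ = 0.65 × 1.125 = 0.731. With n = 1,300 and k = 2, the expected mean squares are 1.731 (breaths), 0.269 (residual) and 1,300 × 0.125 + 0.269 = 162.8 (signal).

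The interval weights the signal mean square by a = 2 × 0.65/(1300 × 0.35) = 0.00286 and the residual by b = 1 + 2 × 0.65 × 1299/(1300 × 0.35) = 4.711. Its denominator degrees of freedom are then (0.465 + 1.266)²/(0.465² + 1.266²/1299) = 13.8, because the signal factor has only one. F(0.975; 1299, 13.8) = 2.52, and the lower limit is 1300(1.731 − 2.52 × 0.269)/[2.52(2 × 162.8 + 1298 × 0.269) + 1300 × 1.731] = 0.35. Without offset the same ICC gives about 1,300 degrees of freedom, F = 1.11 and a lower limit of 0.62.

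In simulation at τ = 0.2 and true ICC 0.50, offsets of 0.1 / 0.2 / 0.3 / 0.5 SD give 21.7 / 15.4 / 4.1 / 0.0% false pass. At 0.5 SD and true ICC 0.65 the planned interval passes 0% and a participant jackknife 95%.

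**Condition-mean model.** This uses 139 breaths per person, mean swings of 1 / 20.1 / 20.1 / 29.1 / 3 mmHg (holds, occluded, inspiratory, expiratory, shallow), between-person SDs of 0.5 / 5.1 / 5.1 / 13.2 / 1.0 and a 25% breath-to-breath CV. The 20.1 and 29.1 are medians from section 9.1.3; 5.1 = (21.9 − 15.0)/1.349 and 13.2 = (38.4 − 20.6)/1.349 come from its quartiles; the rest is assumed. At true ICC 0.50 and τ = 0 / 0.1 / 0.2 / 0.3, false pass is 5.1 / 13.0 / 24.4 / 30.8% without offset. If the device is pressure plus zero-mean noise, variance matching itself leaves an offset of about 0.5 SD, and false pass is 0.0 / 0.0 / 0.1 / 2.6%.

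**Participant jackknife (t, 9 df), scaling within participant, true ICC 0.50.** False pass is 2.7–3.7% with coverage 94–95% in the simple model (including serial correlation and offset), and 2.1–4.6% with 92–94% in the condition-mean model. Section 9.1.3 also says "Periods where the DreamKit device indicates poor effort data quality by means of channel fail events will be excluded from analyses", so counts may be unequal. With very unequal counts false pass is 3.3–4.7% (coverage 93–95%) and 2.3–6.2% (90–93%) respectively.

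**The case against.** The best defence concerns the target of inference. Section 4.1 frames the objective around ten healthy participants, and section 5.2.1 likens the design to a ten-person oximeter validation. Scored against the mean ICC of the ten people studied, the planned interval does well: coverage is 94 / 96 / 93 / 93% at τ = 0 / 0.1 / 0.2 / 0.3, while the jackknife over-covers (95 / 99 / 100 / 100%). The plan never states its target, so the population reading is an inference. It is the reading that fits sections 4.3 and 6.5, and serial correlation matters under either.

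Second, the direction is unknown. The 11% to 30% figures need little offset, yet variance matching can create one, and then the risk is a false fail. This stands.

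Third, the pressures in section 9.1.3 are changes from normal breathing, not peak-to-peak swings, and the inspiratory figure was also applied to occluded breaths. The condition-mean model is therefore only loosely tied to the documents. A rough check that added a baseline swing of 6 to 10 mmHg changed little.

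Fourth, the remedy depends on the unit of scaling, which section 12.2.4 leaves open. With one pooled scale factor, jackknife false pass is 3.0–5.6% in the simple model but up to 15.3% (coverage 84%) in the condition-mean noise model, where the planned interval gives 4.9%. This also stands and shapes the fix.

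**Conclusion.** The concern holds. That clustering is ignored follows directly from the model named in section 12.2.4. How much it matters, and in which direction, depends on between-person variation, serial correlation and mean offset, none of which the documents give.

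Over the assumed ranges, the false-pass rate at the boundary runs from near nominal to about 30% when offset is small, and down to zero when offset is large. In the latter case a device with a true ICC of 0.65 can fail every time. The false-pass excess is confined to the region near 0.5; at a true ICC of 0.40 the simple model never passed more than 3.0%. The upper end (τ = 0.3) is a wide assumption. Because the sole success criterion is affected and the plan has no check on it, the interval should be changed before analysis.

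**What to change.** Keep the ICC point estimate, the 0.5 criterion and ten participants. In section 12.2.4:

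1. State that scaling is done within each participant before pooling, which is the order of steps the section already suggests.
2. Take the deciding lower bound from a participant-level interval. For example, leave out each participant j in turn, redo the scaling and pooled ICC, and form pseudo-values 10z − 9z₍₋ⱼ₎, where z is the Fisher-z ICC. The lower limit is their mean minus 2.262 × SD/√10 (t on 9 df), back-transformed and compared with 0.5.
3. Report the model-based interval as descriptive only.
4. If one pooled scale factor is intended instead, check the chosen interval by simulation before adopting it.

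It would also help to state in section 4.1 that the target is the population of intended users.

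The cost is SAP wording and a short program, with no new data. The pass probability changes as follows (planned interval → jackknife):

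| Setting | True ICC 0.60 | 0.65 | 0.70 |
|---|---|---|---|
| τ = 0.2, no offset | 90 → 47% | 99.6 → 82% | 100 → 97% |
| τ = 0.1, no offset | 98 → 85% | 100 → 99.8% | 100 → 100% |
| τ = 0.1, condition-mean noise model | 5 → 76% | 45 → 96% | 94 → 99.7% |

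Without heterogeneity the loss is small at a true ICC of 0.60 (100 → 99.5%) and larger at 0.55 (74 → 63%). Where people differ, the lost power reflects precision that the planned interval did not have.
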